8.3.1 Method of detecting AEs and SAEs

Care will be taken not to introduce bias when detecting AEs and/or SAEs. Open-ended and non-leading verbal questioning of the patient is the preferred method to inquire about AE occurrences.

8.3.2 Time period and frequency for collecting AE and SAE information

AEs and SAEs will be collected from the time of the patient signing the ICF until 90 days after the last dose of durvalumab. If an event that starts after the defined safety follow-up period noted above is considered to be due to a late onset toxicity to study drug, then it should be reported as an AE or SAE as applicable.

All SAEs will be recorded and reported to the Sponsor or designee within 24 hours, as indicated in [Appendix B](#). The Investigator will submit any updated SAE data to the Sponsor within 24 hours of it being available.

Investigators are not obligated to actively seek AEs or SAEs in former study patients. However, if the Investigator learns of any SAE, including a death, at any time after a patient's last visit and he/she considers the event to be reasonably related to the study treatment or study participation, the Investigator should notify the Sponsor.

The method of recording, evaluating, and assessing causality of AEs and SAEs and the procedures for completing and transmitting SAE reports are provided in [Appendix B](#).

8.3.3 Follow-up of AEs and SAEs

After the initial AE/SAE report, the Investigator is required to proactively follow each patient at subsequent visits/contacts. All AEs, SAEs, and AESIs (as defined in Section [8.3.12](#)) will be followed until resolution, stabilization, the event is otherwise explained, or the patient is lost to follow-up.

Any AEs that are unresolved at the patient's last AE assessment in the study are followed up by the Investigator for as long as medically indicated (this may be beyond the 90 days after the last dose of durvalumab), but without further recording in the CRF. AstraZeneca retains the right to request additional information for any patient with ongoing AE(s)/SAE(s) at the end of the study, if judged necessary.

8.3.4 Adverse event data collection

The following variables will be collected for each AE:

- AE (verbatim)
- The date when the AE started and stopped
- The maximum CTCAE grade reported
- Changes in CTCAE Grade (report only the maximum CTCAE Grade for a calendar day)
- Whether the AE is serious or not
- Investigator causality rating against the IPs (yes or no)
- Action taken with regard to IPs
- Administration of treatment for the AE
- Outcome

In addition, the following variables will be collected for SAEs:

- Date the AE met criteria for SAE

- Date the Investigator became aware of the SAE
- Seriousness criteria
- Date of hospitalization
- Date of discharge
- Probable cause of death
- Date of death
- Whether an autopsy was performed
- Causality assessment in relation to study procedure(s)
- Causality assessment in relation to other medication, as explained in Section 8.3.5
- Description of the SAE

The grading scales found in the revised NCI CTCAE version 5.0 will be utilized for all events with an assigned CTCAE grading. For those events without assigned CTCAE grades, the recommendation in the CTCAE criteria that converts mild, moderate, and severe events into CTCAE grades should be used. A copy of the CTCAE version 5.0 can be downloaded from the Cancer Therapy Evaluation Program website (<http://ctep.cancer.gov>).

It is important to distinguish between serious and severe AEs. Severity is a measure of intensity, whereas seriousness is defined by the criteria in Appendix B 2. An AE of severe intensity need not necessarily be considered serious. For example, nausea that persists for several hours may be considered severe nausea, but not an SAE unless it meets the criteria shown in Appendix B 2. On the other hand, a stroke that results in only a limited degree of disability may be considered a mild stroke, but it would be an SAE if it satisfies the criteria shown in Appendix B 2.

8.3.5 Causality collection

The Investigator will assess causal relationship between IP and each AE, and answer “yes” or “no” to the question “Do you consider that there is a reasonable possibility that the event may have been caused by the IP?”

For SAEs, causal relationship will also be assessed for other medication and study procedures. Note that for SAEs that could be associated with any study procedure the causal relationship is implied as “yes.”

A guide to the interpretation of the causality question is found in Appendix B to the Clinical Study Protocol (CSP).

8.3.6 Adverse events based on signs and symptoms

All AEs spontaneously reported by the patient or reported in response to the open question from the study site staff: “Have you had any health problems since the previous visit/you were last asked?”, or revealed by observation will be collected and recorded in the CRF. When collecting

AEs, the recording of diagnoses is preferred (when possible) to recording a list of signs and symptoms. However, if a diagnosis is known and there are other signs or symptoms that are not generally part of the diagnosis, the diagnosis and each sign or symptom will be recorded separately.

8.3.7 Adverse events based on examinations and tests

The results from the Clinical Study Protocol-mandated laboratory tests and vital signs will be summarized in the clinical study report (CSR). Deterioration as compared to baseline in protocol-mandated laboratory tests and vital signs should therefore only be reported as AEs if they fulfill any of the SAE criteria or are the reason for discontinuation of treatment with the IP.

If deterioration in a laboratory value/vital sign is associated with clinical signs and symptoms, the sign or symptom will be reported as an AE and the associated laboratory result/vital sign will be considered as additional information. Wherever possible, the reporting Investigator uses the clinical rather than the laboratory term (eg, anemia versus low hemoglobin value). In the absence of clinical signs or symptoms, clinically relevant deteriorations in nonmandated parameters should be reported as AE(s).

Deterioration of a laboratory value that is unequivocally due to disease progression should not be reported as an AE/SAE.

Any new or aggravated clinically relevant abnormal medical finding at a physical examination as compared with the baseline assessment will be reported as an AE unless unequivocally related to the disease under study (see Section [8.3.9](#)).

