2.3.2.1 Durvalumab

Risks with durvalumab include, but are not limited to, diarrhea/colitis, pneumonitis/ILD, endocrinopathies (ie, events of hypophysitis/hypopituitarism, adrenal insufficiency, hyper- and hypothyroidism, type I diabetes mellitus, and diabetes insipidus), hepatitis/increases in transaminases, nephritis/increases in creatinine, pancreatitis/increases in amylase and lipase, rash/dermatitis, myocarditis, myositis/polymyositis, infusion-related reactions, hypersensitivity reactions, pancreatitis, serious infections, and other rare or less frequent inflammatory events including neuromuscular toxicities (eg, Guillain-Barre syndrome, myasthenia gravis).

For information on all identified and potential risks with durvalumab, please always refer to the current version of the durvalumab IB.

In monotherapy clinical studies, AEs at an incidence of > 20% include events such as fatigue, cough, decreased appetite, dyspnea, and nausea. Approximately 10% of patients discontinued the drug due to an AE. In the PACIFIC Study in patients with Stage III NSCLC following cCRT, AEs (all causality) experienced during the study with an incidence of > 10% (durvalumab vs

placebo) were cough (35.4% vs 25.2%); fatigue (23.8% vs 20.5%); dyspnea (22.3% vs 23.9%); radiation pneumonitis (20.2% vs 15.4%); diarrhea (18.3% vs 18.8%); pyrexia (14.7% vs 9%); decreased appetite (14.3% vs 12.8%); nausea (13.9% vs 13.2%); pneumonia (13.1% vs 7.7%); pneumonitis (12.6% vs 7.7%); arthralgia (12.4% vs 11.1%); pruritus, rash and upper respiratory tract infection (12.2% each vs 4.7%, 7.3% and 9.8%, respectively); constipation (11.8% vs 8.5%); hypothyroidism (11.6% vs 1.7%); headache (10.9% vs 9.0%); asthenia (10.7% vs 13.2%); and back pain (10.5% vs 11.5%). Combined events of pneumonitis or radiation pneumonitis occurred in 33.9% vs 24.8% of patients, including CTCAE Grade 3 pneumonitis or radiation pneumonitis in 3.4% vs 2.6% of patients; no patients in either treatment group reported Grade 4 events of pneumonitis or radiation pneumonitis.

Please see the current version of the IB for a detailed summary of the monotherapy data including AEs, serious adverse events (SAEs), and CTCAE Grade 3 to 5 events reported across the durvalumab program.

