### 3.2.1 Primary Safety Endpoint

The primary endpoint of this study is the incidence of Grade 3 and Grade 4 PRAEs (see Section 3.2.3.1) which occur within the first six months (ie, up to and including the 183rd day) after the initiation of durvalumab. Any Grade 3 or Grade 4 PRAEs which started after the 183rd day of the study, or after the 90th day following discontinuation of durvalumab, or after the start of subsequent anti-cancer therapy will not be included.

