#### **3.2.3.1 Possibly-Related Adverse Events**

A PRAE is any TEAE with a relatedness to durvalumab of possible, or where the relatedness is missing. When the relatedness of a TEAE is missing on the electronic Case Report Form (eCRF), all efforts will be taken to ensure that the Investigator assigns his/her assessment of relatedness prior to DBL.

If relatedness of a TEAE is missing at the DBL, as given in Section 4.1.2, the TEAE will be considered as possibly related to durvalumab.

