#### 4.5.4 Laboratory Data

Laboratory data obtained up until the 90 days following discontinuation of study treatment or until the initiation of the first subsequent anti-cancer therapy following discontinuation of study treatment (whichever occurs first) will be used for reporting.

Absolute values and change from baseline for all continuous haematology and clinical chemistry laboratory parameters will be summarised by visit. If a patient does not have the baseline value of laboratory data or the value at visit, the change from baseline is considered as missing.

Shift tables for laboratory values by worst CTCAE Grade will be produced, and for specific parameters separate shift tables indicating hyper- and hypo- directionality of change will be produced. The laboratory parameters for which CTCAE Grade shift outputs will be produced are:

- Haematology: Haemoglobin, Leukocytes, Lymphocytes (absolute count), Neutrophils (absolute count), Platelets,
- Clinical chemistry: Alanine transaminase (ALT), Aspartate transaminase (AST), alkaline phosphatase (ALP), Total bilirubin, total protein, Sodium (hypo- and hyper-), Potassium (hypo- and hyper-), Corrected calcium (hypo- and hyper-), Glucose (hypo- and hyper-), and Creatinine

For categorical urinalysis parameters (Bilirubin, Blood, Glucose, Protein), a shift table will be produced comparing baseline value to maximum on-treatment value.

For the parameters with no CTCAE grading that are listed in the CSP the number and percentage of patients with laboratory values outside normal range will be summarized by shift tables from baseline to the post-baseline maximum and minimum value on-treatment.

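### SAP 4.5.4 omits amylase and lipase from its CTCAE grade-shift list, although Protocol 8.3.7 relies on laboratory summaries for symptom-free Grade 3/4 rises that the primary endpoint cannot count

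*Protocol*

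**What the plan says.** **AE reporting.** Protocol 8.3.7 states that results of mandated laboratory tests will be summarised in the study report. It concludes that deterioration in them "should therefore only be reported as AEs if they fulfill any of the SAE criteria or are the reason for discontinuation" of study treatment. If symptoms accompany the abnormal value, "the sign or symptom will be reported as an AE and the associated laboratory result/vital sign will be considered as additional information". Parameters that the protocol does not mandate follow a different rule: clinically relevant worsening in them is an AE.

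**Primary endpoint.** SAP 3.2.1: "The primary endpoint of this study is the incidence of Grade 3 and Grade 4 PRAEs", counted to Day 183. SAP 3.2.3.1: "A PRAE is any TEAE with a relatedness to durvalumab of possible, or where the relatedness is missing".

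**Named risks.** Protocol 2.3.2.1 includes among the risks of durvalumab "hepatitis/increases in transaminases, nephritis/increases in creatinine, pancreatitis/increases in amylase and lipase".

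**Measurement.** Protocol Table 8 makes amylase and lipase part of clinical chemistry and accepts one of the two at sites that routinely measure only one. SAP 3.2.6 schedules amylase and/or lipase at screening and on Day 1 of each cycle.

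**Laboratory outputs.** SAP 4.5.4 introduces a closed list with the words "The laboratory parameters for which CTCAE Grade shift outputs will be produced are". It names five haematology and ten chemistry parameters. The same section summarises values and changes from baseline by visit for every continuous chemistry parameter. It adds an out-of-range shift table for protocol parameters that have no CTCAE grading.

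**The concern.** The protocol takes a class of findings out of AE reporting on the ground that the laboratory summaries will show them. That is a sound arrangement only if those summaries show how many patients reached Grade 3 or 4. For one of the risks the protocol names, increases in amylase and lipase, the SAP does not specify such a count.

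At stake is the completeness of the safety description. The trial's main result is a rate of Grade 3/4 related events within six months. A reader of the report would need the laboratory tables to learn about graded pancreatic enzyme rises that were managed, for example, by a dose delay and so never became AEs.

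**Working it through.** **1. The plan's own figure.** Protocol Table 11 and SAP Table 1 give 5.0 to 23.0 for 12% with n = 60. With x = 60 × 0.12 = 7.2, the Clopper-Pearson limits are the 2.5% quantile of Beta(x, n − x + 1) and the 97.5% quantile of Beta(x + 1, n − x). These give 5.0% to 23.0%, as stated. The whole-patient count 7/60 = 11.7% gives 4.8% to 22.6%. Nothing in this point disturbs that calculation.

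**2. Can a symptom-free Grade 3/4 rise in a mandated test count in the primary endpoint?** A PRAE must be a treatment-emergent AE. Under 8.3.7 a mandated laboratory value becomes an AE only by being serious or by stopping treatment. Neither CTCAE grade nor dose delay is a trigger. A non-serious Grade 3/4 rise that leaves treatment running is therefore not an AE, not a PRAE, and not in the endpoint, even if the investigator attributes it to durvalumab.

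**3. Which named laboratory risks get a count by grade in SAP 4.5.4?**

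| Risk named in Protocol 2.3.2.1 | On CTCAE shift list? | Other patient-level output |
|---|---|---|
| Transaminases | Yes (ALT, AST) | Counts by multiple of the upper limit of normal, plots and narratives (SAP 4.5.4.1) |
| Creatinine | Yes | Renal impairment categories (SAP 4.5.4.3) |
| Amylase, lipase | No | None specified by grade |

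The list is haemoglobin, leukocytes, lymphocytes, neutrophils and platelets (5), plus ALT, AST, ALP, total bilirubin, total protein, sodium, potassium, corrected calcium, glucose and creatinine (10). Amylase and lipase account for 0 of the 15.

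**4. What remains for amylase and lipase?**
- By-visit summaries (SAP 4.5.4, statistics in 4.1.1): n, mean, standard deviation, median, minimum and maximum. A maximum can reveal an extreme value, but not how many patients reached Grade 3/4. Under SAP 4.1.4.1 the value nearest the scheduled date represents the visit, so an unscheduled peak may not appear there.
- Patient listings (SAP 4.1.1): all collected values, uncounted.
- The out-of-range shift table: this depends on CTCAE version 5.0, whose content the documents do not reproduce. If it grades these enzymes, they miss both shift tables. If it does not, they fall into the out-of-range table.

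**5. Time window.** SAP 4.5.4 uses laboratory data until 90 days after discontinuation or first subsequent anti-cancer therapy. The primary endpoint stops at Day 183. Even for the listed parameters, the shift tables do not show what happened within six months.

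**6. Scale only.** The documents give no rate of laboratory-only Grade 3/4 events. One patient is 1/102 = 0.98 percentage points overall, 1/59 = 1.7 in the standard cohort and 1/43 = 2.3 in the palliative cohort. Take 12/102 as an assumed starting count, and suppose k further patients had only a related laboratory finding:

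| k | Rate | Exact 95% CI |
|---|---|---|
| 0 | 11.8% | 6.2 to 19.6 |
| 1 | 12.7% | 7.0 to 20.8 |
| 3 | 14.7% | 8.5 to 23.1 |
| 5 | 16.7% | 10.0 to 25.3 |

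Here k = 0 is as compatible with the documents as k = 5.

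**The case against.** The strongest reply is that the plan does this deliberately and openly. The endpoint is related adverse events, not all toxicity, and 8.3.7 says where laboratory results go instead. Several routes into AE reporting also remain. Symptoms are recorded as AEs. A medically important value can meet an SAE criterion (Appendix B 2 and B 5). Potential Hy's Law cases are reported as related SAEs (Appendix E 4.2). Pancreatic events are a prespecified category of special or possible interest (SAP 3.2.3.2). Appendix B 1 even gives an abnormal laboratory finding as an example of an AE, although 8.3.7 is the more specific rule for mandated tests.

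Much of this stands, and it rules out three stronger readings that a reader might infer.

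- *That the named laboratory risks in general go ungraded.* They do not: transaminases and creatinine are on the shift list and have further outputs.
- *That amylase and lipase drop out of the laboratory reporting altogether.* They do not: they stay in the by-visit summaries and the listings.
- *That a 12% rate would really be about 15% to 18%.* That needs an assumed 3 to 6 further patients in 102, all judged related and none already counted. The documents support none of these assumptions. Nor do they say whether the 12% reference was collected under the same reporting rule.

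The reply does not supply a count of patients with Grade 3/4 amylase or lipase values.

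**Conclusion.** The point holds in a narrow form. A symptom-free, non-serious Grade 3/4 rise in a mandated test that does not stop treatment is outside the primary endpoint by design. For transaminases, bilirubin and creatinine the SAP makes good on the protocol's promise with grade-shift tables. For amylase and lipase, if CTCAE version 5.0 grades them, no planned table counts the patients affected. If it does not, the out-of-range shift table applies and the gap largely closes.

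The size of any undercount cannot be computed from the documents and may be zero. The primary estimate as defined is not in error. The step from this gap to a combined rate of PRAEs or any Grade 3/4 laboratory value is also not warranted. Laboratory values carry no causality assessment, and Exclusion Criterion 10 admits patients with unresolved lymphopenia after earlier therapy, so a composite could absorb unrelated values. Minor, and cheap to put right.

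**What to change.** - Add amylase and lipase to the CTCAE shift list in SAP 4.5.4, overall and by cohort. Use the number of patients tested for each enzyme as its denominator, since a site may measure only one. This agrees with Protocol 9.5.2.1, which restricts laboratory denominators to evaluable patients. If CTCAE version 5.0 proves not to grade them, say so and confirm that they are in the out-of-range shift table.
- Optionally, add a laboratory-only count of patients with a new or worsened Grade 3/4 value by Day 183, overall and by cohort. Define new or worsened against baseline, label the count as carrying no causality assessment, and do not combine it with the PRAE rate.
- Leave AE collection and the primary endpoint as they are.

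The cost is two more shift parameters and, if wanted, one more table, all from data already collected. The downside is slightly more output and laboratory counts that will include values unrelated to durvalumab.

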8.3.8 Hy's Law

Cases where a patient shows elevations in liver biochemistry may require further evaluation and occurrences of AST or ALT $\geq 3 \times \text{ULN}$ together with TBL $\geq 2 \times \text{ULN}$ may need to be reported as SAEs. Please refer to [Appendix E](#) for further instruction on cases of increases in liver biochemistry and evaluation of Hy's Law.

8.3.9 Disease progression

Disease progression can be considered as a worsening of a patient's condition attributable to the disease for which the IP is being studied. It may be an increase in the severity of the disease under study and/or increases in the symptoms of the disease. The development of new or progression of existing metastasis to the primary cancer under study should be considered as disease progression and not an AE. Events which are unequivocally due to disease progression should not be reported as an AE during the study.

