Table 2 Schedule of activities for patients who have discontinued study drug or completed treatment with study drug

Evaluation	Time since last dose of durvalumab								For details, see Section	
	Day (± 3)	Months (± 1 week)						12 months and every 3 months (± 2 weeks)		
	30	2	3	4	6	8	10			
Physical examination (full)	X								8.2.2	
Vital signs	X								8.2.3	
Body weight	X	X	X						8.2.3	
Pregnancy test ^a	X	As clinically indicated							8.2.1	
AE/SAE assessment	X	X	X						8.3	
Concomitant medications	X	X	X						6.4	
WHO/ECOG PS ^b	At timepoints consistent with tumor assessments; at 30, 60, and 90 days after last dose; and then at initiation of subsequent anticancer therapy								8.2.6	
Subsequent anticancer therapy ^{c,d}	← →									
Survival status ^e		X	X	X	X	X	X		8.1.1	
Hematology	X	X	X						8.2.1	
Clinical chemistry	X	X	X						8.2.1	
Urinalysis	As clinically indicated								8.2.1	
TSH (reflex free T3 or free T4) ^f	X	X	X						8.2.1	
CCI [REDACTED]		X	X	X					8.1.2.1, 8.1.2.2, 8.1.2.3, 9.5.2.3	
Tumor assessment as per local institutional standard care (RECIST 1.1) ^h	Additional scans to be completed per standard practice post progression. Patients who permanently discontinue IP for reasons other than objective RECIST 1.1 disease progression should continue to have RECIST 1.1 assessments performed q8w \pm 1 week beginning 8 weeks after IP treatment initiation for the first 48 weeks (relative to the first dose) and q12w \pm 1 week thereafter until clinical progression/deterioration or RECIST 1.1-defined radiological progression plus one or more additional follow-up scans for confirmation of progression until confirmed radiological progression, the end of study, death, study discontinuation, or Sponsor decision (whichever comes first).								8.1, Appendix F	

AE = Adverse event; CT = Computed tomography; eCRF = Electronic case report form; CCI [REDACTED]

CCI

= Investigational product; IV = Intravenous; MRI = Magnetic resonance imaging; NSCLC = Non-small cell lung cancer; PD = Progressive disease; **CCI** [REDACTED]; IP

CCI

CCI [REDACTED]; q8w, q12w = Every 8, 12 weeks, respectively; RECIST 1.1 = Response Evaluation Criteria in Solid Tumors version 1.1; SAE = Serious adverse event; T3 = Triiodothyronine; T4 = Thyroxine; TSH = Thyroid-stimulating hormone; WHO/ECOG PS = World Health Organization/Eastern Cooperative Oncology Group Performance Status.

- ^a For women of childbearing potential only. A urine or serum pregnancy test is acceptable.

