6.1.3 Duration of treatment and criteria for treatment through progression

Treatment will be administered beginning on Day 1 for 12 months for durvalumab monotherapy or until clinical progression or RECIST 1.1-defined radiological progression (refer to [Appendix F](#)) unless there is unacceptable toxicity, withdrawal of consent, or another discontinuation criterion is met.

During the treatment period, patients who are clinically stable at an initial RECIST 1.1-defined PD may continue to receive study treatment at the discretion of the Investigator and patient as long as they are deemed to be receiving clinical benefit. A follow-up scan is to be collected after the initial RECIST 1.1-defined PD, 4-8 weeks after the prior assessment of PD; this follow-up scan is evaluated using the post-progression evaluation criteria outlined in [Appendix F](#). Patients with confirmed PD who continue to receive durvalumab at the discretion of the Investigator and patient (following consultation with AstraZeneca) can receive treatment for the remainder of the 12-month treatment period, and image acquisitions and tumor assessments should continue on their regular imaging schedule for the duration of treatment.

Patients with rapid tumor progression or with symptomatic progression that requires urgent medical intervention (eg, central nervous system metastasis, respiratory failure due to tumor compression, or spinal cord compression) will not be eligible for continuing durvalumab.

For all patients who are treated through progression, the Investigator should ensure that:

- The patient does not have any significant, unacceptable, or irreversible toxicities that indicate continuing treatment will not further benefit the patient. The patient must not have experienced a toxicity that required permanent discontinuation of study treatment.
- There is absence of clinical symptoms or signs indicating clinically significant disease progression accompanied by a decline in WHO/ECOG PS to > 2.
- There is absence of rapid disease progression or threat to vital organs or critical anatomical sites (eg, central nervous system metastasis, respiratory failure due to tumor compression, or spinal cord compression) requiring urgent alternative medical intervention.
- The patient still fulfills the eligibility criteria for this study (see Section 5.1 and 5.2) with the exception of inclusion criteria 9, 11, and 14 and exclusion criterion 17.

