8.2.6 World Health Organization/Eastern Cooperative Oncology Group performance status

WHO/ECOG PS will be assessed at the times specified in the assessment schedules (see the SoAs) based on the following:

- 0 Fully active; able to carry out all usual activities without restrictions
- 1 Restricted in strenuous activity, but ambulatory and able to carry out light work or work of a sedentary nature (eg, light housework or office work)
- 2 Ambulatory and capable of self-care, but unable to carry out any work activities; up and about more than 50% of waking hours
- 3 Capable of only limited self-care; confined to bed or chair more than 50% of waking hours
- 4 Completely disabled; unable to carry out any self-care and totally confined to bed or chair
- 5 Dead

Any significant change from baseline or screening must be reported as an AE.

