Appendix B Adverse event definitions and additional safety information

B 1 Definition of adverse events

An adverse event (AE) is the development of any untoward medical occurrence (other than progression of the malignancy under evaluation) in a patient or clinical study patient administered a medicinal product and which does not necessarily have a causal relationship with this treatment. An AE can therefore be any unfavorable and unintended sign (eg, an abnormal laboratory finding), symptom (for example nausea, chest pain), or disease temporally associated with the use of a medicinal product, whether or not considered related to the medicinal product.

The term AE is used to include both serious and nonserious AEs and can include a deterioration of a pre-existing medical occurrence. An AE may occur at any time, including run-in or washout periods, even if no study treatment has been administered.

B 2 Definitions of serious adverse events

A serious adverse event (SAE) is an AE occurring during any study phase (ie, run-in, treatment, washout, follow-up), that fulfills one or more of the following criteria:

- Results in death
- Is immediately life-threatening
- Requires in-patient hospitalization or prolongation of existing hospitalization
- Results in persistent or significant disability or incapacity
- Is a congenital abnormality or birth defect
- Is an important medical event that may jeopardize the patient or may require medical treatment to prevent one of the outcomes listed above

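### Section 8.2.6 has no progression exception, so a performance-status decline unequivocally due to progression is an AE under that section but not under Section 8.3.9

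*Protocol*

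**What the plan says.** Protocol Section 8.3.9 keeps progression out of AE reporting: "Events which are unequivocally due to disease progression should not be reported as an AE during the study". Appendix B 1 supports this by defining an AE as "any untoward medical occurrence (other than progression of the malignancy under evaluation") in a patient given a medicinal product.

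Section 8.3.7 repeats the exception for two kinds of data. For laboratory values: "Deterioration of a laboratory value that is unequivocally due to disease progression should not be reported as an AE/SAE". For new or aggravated physical findings: such a finding "will be reported as an AE unless unequivocally related to the disease under study", with a pointer to Section 8.3.9. Section 8.3.11 makes a similar distinction for deaths, since a death clearly resulting from progression is not reported as an SAE.

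Section 8.2.6, on WHO/ECOG PS, says: "Any significant change from baseline or screening must be reported as an AE". It has no exception and no cross-reference, and it does not define a significant change.

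The SAP (Section 3.2.3) sends every treatment-emergent AE to the summaries in Section 4.5.1. Those include tables of all AEs and of all Grade 3 or 4 AEs regardless of causality. Protocol Section 9.4 lists both as outcome measures, and SAP Section 4.1.1 has safety data summarised overall and by radiotherapy cohort. The SAP has no rule for PS events recorded at progression.

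**The concern.** The two instructions meet in a case that the protocol foresees. Section 6.1.3, on treatment through progression, refers to "clinically significant disease progression accompanied by a decline in WHO/ECOG PS to > 2". PS is recorded at every cycle (Table 1). After the last dose it is recorded as follows: "At timepoints consistent with tumor assessments; at 30, 60, and 90 days after last dose" (Table 2). Many of the visits at which progression is found are therefore visits at which PS is also scored.

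A site that follows 8.2.6 literally records the decline as an AE. A site that follows 8.3.9 does not. The all-cause tables would then mix disease progression with toxicity to a degree set by site habit. The trial has one arm, so no control group shows how much of an AE rate is progression. Efficacy failure is already counted in PFS and OS and should not appear a second time as an adverse event.

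**Working it through.** The documents state no figure on this point, so there is none to reproduce. The check sets the rules side by side and then works out what one affected patient does to a percentage.

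**Step 1. Which rule applies to which observation.**

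| Observation, unequivocally due to progression | Governing text | Reported as AE? |
|---|---|---|
| Laboratory deterioration | 8.3.7 | No |
| Physical finding | 8.3.7, pointing to 8.3.9 | No |
| Any event | 8.3.9; Appendix B 1 | No |
| Significant PS change | 8.2.6 | Yes |
| Significant PS change | 8.3.9; Appendix B 1 | No |

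The last two rows conflict. If the cause is equivocal there is no conflict, because 8.3.9 does not apply and both routes lead to an AE.

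**Step 2. When the event can reach a table.** AEs are collected until 90 days after the last dose (Protocol 8.3.2). SAP 4.5.1 by default stops the summaries at 90 days or at the first subsequent therapy, whichever comes first. PS visits tied to tumour assessments can fall later than that, and those do not feed the summaries. The exposed events are declines after the first dose, within 90 days of the last dose, and before subsequent therapy.

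**Step 3. Which tables.** The event enters the all-AE tables, and it can add a line of its own in the tables by preferred term. For the Grade 3/4 tables it must be graded 3 or 4. For events without an assigned CTCAE grade, Section 8.3.4 says that the recommendation "that converts mild, moderate, and severe events into CTCAE grades should be used", so a decline judged severe can be graded that way.

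**Step 4. Size per patient.** Denominators are the approximate numbers treated in Protocol 9.2 and SAP 1.3: 59 standard + 43 palliative = 102.

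- Overall: 1/102 = 0.98 points
- Standard cohort: 1/59 = 1.7 points
- Palliative cohort: 1/43 = 2.3 points

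A patient moves the any-AE row only if they have no other AE, and the any-Grade-3/4 row only if they have no other Grade 3/4 AE.

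**Step 5. Illustration on assumed inputs.** The documents give neither a base all-cause Grade 3/4 rate nor a number of affected patients. Assume a base of 31/102 and add patients who count only because of 8.2.6. Intervals are exact (Clopper-Pearson) 95% CIs; the same method reproduces the plan's own precision table, for example 5.0 to 23.0 for 12% of 60.

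| Extra patients (assumed) | Rate | 95% CI |
|---|---|---|
| 0 | 31/102 = 30.4% | 21.7 to 40.3 |
| 1 | 32/102 = 31.4% | 22.5 to 41.3 |
| 5 | 36/102 = 35.3% | 26.1 to 45.4 |
| 10 | 41/102 = 40.2% | 30.6 to 50.4 |

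**Step 6. Primary endpoint.** It counts Grade 3 or 4 possibly related events up to day 183 (SAP 3.2.1 and 4.3). Appendix B 7 directs that deterioration of the disease under study through lack of effect be classed as having no reasonable possibility of a causal link. Such an event reaches the endpoint only if the investigator still marks it related, or if causality is missing at database lock, which SAP 3.2.3.1 and 4.1.2 count as related.

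**The case against.** The best defence is that Section 8.3 refers AE definitions to Appendix B, whose definition leaves out progression, and that 8.3.9 counts worsening disease symptoms as progression. A site could sensibly read 8.2.6 inside that definition. Section 8.3.6 also prefers a diagnosis to a sign, and where the diagnosis is progression, 8.3.9 removes it. This is a fair reading, but nothing in the protocol makes it the required one. Section 8.2.6 says *must*, and 8.3.7 shows that the exception was written out where it was wanted.

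Several stronger readings are not supported:

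- **That the primary endpoint is contaminated.** Appendix B 7 largely prevents this; only the two routes in Step 6 remain.
- **That a PS improvement must be reported.** Section 8.2.6 gives no direction of change, but an AE has to be untoward under Appendix B 1.
- **That PS 3 or 4 automatically becomes Grade 3 or higher.** Section 8.3.4 converts severity into grades; it does not map PS levels to grades.
- **That Section 6.1.3 makes PS decline a sign of progression in its own right.** It shows only that the two can occur together.
- **That one radiotherapy cohort is distorted more.** The documents give no progression rates by cohort.
- **That a definite share of patients is affected.** Multiplying a guessed progression rate by a guessed rate of PS loss uses two figures found in neither document. It would also overstate the shift, because patients who already have another qualifying event do not change the count.

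**Conclusion.** The contradiction is in the current text, which is wrong as written, but it is narrow. It concerns PS declines that are unequivocally due to progression and fall inside the AE summary window. It affects secondary, descriptive safety tables: all-cause AEs, and all-cause Grade 3/4 AEs if the event is graded so.

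The total effect cannot be stated from the documents. The per-patient effect is 0.98 points overall, 1.7 in the standard cohort and 2.3 in the palliative cohort, on the approximate numbers treated and for a patient with no other qualifying event. The primary endpoint moves only through an event marked related or one with missing causality. The point is worth acting on because a single-arm safety trial has no comparator to reveal the misclassification and the remedy is close to free.

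**What to change.** Reconcile Section 8.2.6 with Section 8.3.9, for example: *A clinically significant worsening of WHO/ECOG PS must be reported as an AE, under the underlying diagnosis where there is one (Section 8.3.6), unless it is unequivocally due to progression of the disease under study (see Section 8.3.9).* This limits the rule to worsening and gives PS the exception that 8.3.7 already gives laboratory and physical findings.

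Before database lock, query AE records whose only term is a PS change, and ask the site whether the change was unequivocally due to progression, so that all sites are handled alike. Check at the same time that causality is filled in. Add a line to SAP Section 4.5.1 saying how these records are treated. The query also supplies the count that the documents lack.

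The cost is one sentence in the protocol or a letter to sites, one line in the SAP, and a short data query. No treatment rule, visit or sample size changes. The query matters most if enrolment is already complete, because rewording the protocol does not correct events already recorded and the SAP (Section 5) still plans a final analysis.
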